10.2 Methods Of Efficacy Analysis

The ORR and CBR will be summarized with frequencies and percentages. The exact 95% confidence interval (CI) via the Clopper-Pearson method will be constructed for the ORR and CBR.

A waterfall plot will plot the best percentage change from baseline (or maximum decrease from baseline) in sum of the longest diameters (short axis for measurable lymph node) of target lesions for each subject, plotted in order from greatest percentage change to smallest. The OP-1250 dose will be presented in the plot with different colors. Changes in tumor burden by time point may be summarized.

A swimmer's plot will display overall tumor response over time and include prior therapies in the advanced setting. Patients will be grouped by OP-1250 dose.

[REDACTED]

10.3 Baseline Values

For efficacy purposes, baseline is defined as the last disease assessment conducted on or before the date of first dose of study drug.

10.4 Adjustments for Covariates

No adjustments for covariates are planned.

10.5 Handling of Dropouts or Missing Data

No imputation will be done for missing disease assessments.

10.6 Interim Analysis and Data Monitoring

No formal interim analysis will be conducted.

[REDACTED]

[REDACTED]

10.8 Multiple Comparison/Multiplicity

No adjustments for multiplicity will be made in this study.

10.9 Multicenter Studies

Differences in response by center will not be prospectively analyzed for this preliminary evaluation of efficacy of OP-1250.

[REDACTED]

[REDACTED]

[REDACTED]

[REDACTED]

[REDACTED]

[REDACTED]

12. PHARMACOKINETIC ANALYSES

The PK analyses will be described in a separate PK analysis plan.

13. SAFETY ANALYSES

Dose-limiting toxicities will be summarized in the DLT evaluable analysis set. All other safety analyses will be based on the safety analysis set.

13.1 Dose-Limiting Toxicity

Subjects must receive at least 75% (21 days) of planned OP-1250 dose in Cycle 1 in order to be evaluated for determination of DLTs. Subjects receiving less than 75% of the planned dose for reasons other than experiencing a DLT will be replaced in the dose escalation part of the study. Subjects who receive less than 75% of the study drug due to occurrence of a DLT are considered DLT evaluable and will not be replaced. (Subjects receiving less than 75% of the planned dose in Cycle 1 for reasons other than experiencing a DLT will be evaluated in the overall safety analysis but not for the purpose of dose escalation).

A DLT is defined as the occurrence of any of the following treatment-emergent adverse events (TEAE) graded using NCI-CTCAE v5.0 during Cycle 1 except those that are clearly and incontrovertibly due to disease progression or extraneous causes:

- Any death not clearly due to the underlying disease or extraneous causes
- Grade ≥ 3 non-hematologic toxicity (unless otherwise noted below)
- Grade ≥ 3 nausea and/or vomiting and/or Grade 3 diarrhea not resolving within 72 hours with optimal treatment
- Grade 3 neutropenia accompanied with fever and/or infection
- Grade 3 thrombocytopenia associated with bleeding
- Grade ≥ 4 hematologic toxicity
- Aspartate aminotransferase (AST) or alanine aminotransferase (ALT) $> 3\times$ the upper limit of normal (ULN) and a total bilirubin $> 2\times$ ULN without initial findings of cholestasis (elevated serum alkaline phosphatase) and no other reason for the increase in transaminases and total bilirubin
- AST or ALT $> 8\times$ ULN or AST or ALT $> 5\times$ ULN for ≥ 14 days
- AST or ALT $> 3\times$ ULN with the appearance of fatigue, nausea, vomiting, right upper quadrant pain or tenderness, fever, rash, and/or eosinophilia ($> 5\%$)
- Grade ≥ 3 blurred vision or retinopathy
- Grade ≥ 3 fatigue that does NOT resolve to grade ≤ 1 within 7 days
- Grade ≥ 2 TEAEs that result in omission of treatment for ≥ 7 days during Cycle 1 or delay of Cycle 2 for ≥ 7 days

Multiple concurrent AEs in a single subject leading to DLT will be considered a single DLT.

The MTD is defined as the highest feasible dose tested in which fewer than 33% of subjects experienced a DLT attributable to the study drug, when at least 6 subjects were treated at that dose and were assessable for toxicity.

13.2 Adverse Events

Adverse events will be collected from the time of signing of the informed consent until 30 days following the last dose of study treatment or until resolution/stabilization of any ongoing drug related AEs.

All AE summaries will be restricted to TEAEs, which are defined as those AEs with onset or worsening after the first administration of study drug till the 30 days following the last dose of study drug or any study drug related AEs. [Appendix A](#) contains rules for how partial dates will be handled. If it cannot be determined whether the AE is treatment emergent due to a partial onset date, then it will be counted as such. Verbatim terms in the eCRFs will be mapped to (PT and SOC using MedDRA. Adverse events will be assigned a severity grade per NCI-CTCAE version 5.0. For summaries of maximum CTCAE grade, at each level of subject summarization, a subject is classified according to the highest grade if the subject reported 1 or more events. For summaries of TEAEs that are related to OP-1250, a TEAE is considered related to OP-1250 if it is reported by the Investigator as related, probably related, or possibly related.

AE summaries will be presented by OP-1250 dose using SAF set. Summaries that are displayed by SOC and PTs will be ordered by descending frequency of the total column by SOC and by descending frequency of PT within SOC. Summaries of the following types will be presented:

- Overall summary of TEAEs that contain an overview of each item below.
- Subject incidence of DLTs and total number of unique DLTs by MedDRA SOC and PT in the DLT evaluable analysis set.
- Subject incidence of TEAEs and total number of unique TEAEs by MedDRA SOC and PT.
- Subject incidence of grade 3 or greater TEAEs and total number of unique grade 3 or greater TEAEs by MedDRA SOC and PT.
- Subject incidence of OP-1250-related TEAEs and total number of unique OP-1250-related TEAEs by MedDRA SOC and PT.
- Subject incidence of grade 3 or greater OP-1250-related TEAEs and total number of unique grade 3 or greater OP-1250-related TEAEs by MedDRA SOC and PT.
- Subject incidence of TEAEs by MedDRA SOC, PT, and maximum CTCAE grade.
- Subject incidence of serious TEAEs and total number of unique serious TEAEs by MedDRA SOC and PT.
- Subject incidence of OP-1250-related serious TEAEs and total number of unique OP-1250-related serious TEAEs by MedDRA SOC and PT.
- Subject incidence of TEAEs leading to death as an outcome by MedDRA SOC and PT.
- Subject incidence of TEAEs leading to OP-1250 treatment discontinuation, dose reduction and drug withheld by MedDRA SOC and PT.

If any adverse events of special interest (AESI) are identified throughout the study, subject incidence of each AESI and the total number of unique AESIs will be presented.

Separate listings of all SAEs, all AEs leading to OP-1250 treatment discontinuation, and all AEs resulting in death will be provided. A listing of all deaths will also be presented.

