### 8.8.4 Recommended Phase II Dose

Following Phase 1a dose escalation of OP-1250 from 30 mg to 300 mg QD, a recommended phase 2 dose (RP2D) range was defined of 60 to 120 mg QD. Sixty patients are planned for Phase 1b enrollment, with 30 patients at each dose level (60 and 120 mg). At 60 mg and 120 mg, OP-1250 demonstrated high oral bioavailability and dose proportional exposure. At 120 mg, OP-1250 consistently exceeded the predicted efficacy plasma concentration thresholds from preclinical models. Safety data from 37 patients enrolled in Phase 1b indicated no clinically meaningful difference in the frequency of TEAEs between the 2 dose levels (60 mg,

120 mg) as the most common TEAEs ( $\geq 10\%$ ) were nausea (28%, 21%), vomiting (17%, 16%), fatigue (17%, 5%), and headache (11%, 11%), respectively. Most events were Grade 1 or 2, with the exception of two Grade 3 events at 60 mg (diarrhea and anemia). There were no dose reductions or discontinuations due to an AE. Based on safety and pharmacokinetic data from Study OP-1250-001, 120 mg OP1250 QD has been selected as the RP2D.

Since the RP2D has been determined, active subjects enrolled on the Phase I part of the study may be treated at the RP2D with approval of the Medical Monitor if the investigator or designee considers this in the best interest of the subject.

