3. STUDY ENDPOINTS

The study endpoints of each of the 2 phases of the study are:

Phase I (Dose Escalation and Expansion)

Primary Endpoints:

- Incidence and nature of DLTs as defined in the protocol.
- MTD and/or RP2D of OP-1250 when used as a single agent.
- Incidence, nature, and severity of treatment-emergent Adverse Events (TEAEs) and serious adverse events (SAEs) according to NCI-CTCAE version 5.0.
- Plasma levels of OP-1250 at pre-defined intervals to establish PK parameters (includes maximum concentration (C_{max}), minimum concentration (C_{min}), time to maximum concentration (T_{max}), area under the curve (AUC), half-life (t_{1/2}), and OP-1250 trough concentration at steady state).

Secondary Endpoints:

- ORR by evaluation of tumor response assessments using RECIST 1.1 in subjects with measurable disease.
- CBR as defined by percent of subjects with CR + PR + SD \geq 24 weeks, by evaluation of tumor response assessments using RECIST 1.1.

• [REDACTED]

[REDACTED]

- [REDACTED]
- [REDACTED]
- [REDACTED]
- [REDACTED]
- [REDACTED]
- [REDACTED]

Phase II

Primary Endpoints:

- ORR by evaluation of tumor response assessments using RECIST 1.1 in subjects without evidence of CNS metastases who have measurable disease.
- Incidence, nature, and severity of TEAEs and SAEs according to National Cancer Institute-Common Terminology Criteria for Adverse Events (NCI-CTCAE) version 5.0.
- Plasma levels of OP-1250 at pre-defined intervals to establish PK parameters (includes C_{max}, C_{min}, T_{max}, AUC, t_{1/2}, and OP-1250 trough concentration at steady state). The results of those analyses will be reported separately in PK report.

Secondary Endpoints:

- CBR as defined by percent of subjects with a CR + PR + SD for ≥ 24 weeks, by evaluation of tumor response assessments using RECIST 1.1 in subjects without evidence of CNS metastases.

█

████████████████████

█

█

█

█

█

█

█

█

█

█

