6. GENERAL ANALYSIS CONSIDERATIONS

6.1 Statistical Analysis Cohorts

Statistical analysis will be conducted in the cohorts below.

1. Dose Escalation subjects: All endpoints [REDACTED] will be summarized by dose groups.
2. Subjects treated at 60 mg or 120 mg pooled from dose escalation, dose expansion and phase II (without cohort C): The study subjects and demographic, pharmacodynamic endpoints, and efficacy endpoints will be analyzed by dose groups.

- [REDACTED]
4. All subjects: All safety related endpoints will be summarized based on the safety analysis set by dose groups, [REDACTED] and overall.

For summary by dose groups, the dose groups will be based on the first doses the subjects received.

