13.3 Extent of Exposure

The analysis will be conducted using SAF set.

Study drug exposure will be summarized using the total number of doses received, total number of cycles, duration of study treatment, relative dose intensity, number of dose interruption, and number of dose reduction. Duration of treatment in weeks is defined as the (last dose date - the first dose date + 1)/7. Relative dose intensity will be calculated as the total amount of dose received divided by (the duration on treatment (in days) × assigned dose). The number of subjects with dose interruption, dose reduction and the reason of dose interruption, dose reduction, the number of dose interruptions and dose reductions will be summarized by frequencies and percentages.

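### TEAE incidence by dose (SAP 13.2) is counted over each subject's own treatment time, with no exposure-adjusted or common-window summary; a few added tables would make doses comparable

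*SAP*

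**What the plan says.** SAP section 3 lists among the primary endpoints "Incidence, nature, and severity of treatment-emergent Adverse Events (TEAEs) and serious adverse events (SAEs) according to NCI-CTCAE version 5.0", for Phase I and again for Phase II. SAP 6.1 pools everyone for safety: "All safety related endpoints will be summarized based on the safety analysis set by dose groups". SAP 13.2 repeats the grouping ("AE summaries will be presented by OP-1250 dose using SAF set") and sets the measure, for example "Subject incidence of TEAEs and total number of unique TEAEs by MedDRA SOC and PT". The Grade 3 or higher, related and serious tables have the same form.

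A TEAE is an event with onset or worsening from first dose to 30 days after last dose; drug-related events also count after that (SAP 13.2). Treatment has no fixed length: it continues to progression, toxicity or another stopping reason, for a year or longer (Protocol 8.11, SAP section 4).

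Exposure is derived separately in SAP 13.3: "Duration of treatment in weeks is defined as the (last dose date - the first dose date + 1)/7". It is summarised but not used as a denominator for adverse events. Neither Protocol 11.2 nor SAP section 13 plans a person-time rate, a time-to-first-event summary or a fixed-window incidence for TEAEs.

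On grouping, SAP 6.1 says: "For summary by dose groups, the dose groups will be based on the first doses the subjects received". Protocol 8.8.4 says that "active subjects enrolled on the Phase I part of the study may be treated at the RP2D with approval of the Medical Monitor", which that section sets at 120 mg.

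**The concern.** A subject percentage compares doses fairly only if subjects at each dose were watched for about the same time. Here a subject's window lengthens with time on drug. A dose group with longer treatment, including one that controls disease longer, collects more subjects with at least one event even if the underlying rate is the same. A group with shorter treatment looks safer.

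Several features allow time on treatment to differ by dose group. Phase II is run only at the RP2D, so it adds subjects to 120 mg alone. The 60 mg group comes from Phase I, and the remaining levels come from Part A only. The SAP also provides for subjects still on treatment at data cutoff (SAP 10.1, definition of treatment duration), whose windows are cut short.

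By-dose TEAE percentages do get compared: Protocol 8.8.4 says that data from 37 Phase 1b patients "indicated no clinically meaningful difference in the frequency of TEAEs between the 2 dose levels". The final tables would invite the same kind of reading from the pooled safety set. First-dose grouping adds a second problem: events at 120 mg after a Phase I subject moves to the RP2D are counted under the lower or higher dose first received.

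**Working it through.** **1. The protocol's own by-dose figures.** Protocol 8.8.4 gives, for 60 and 120 mg, nausea 28% and 21%, vomiting 17% and 16%, fatigue 17% and 5%, headache 11% and 11%, in 37 patients. Of all splits of 37, only 18 and 19 reproduces all eight as simple proportions: 5/18, 3/18, 3/18, 2/18 and 4/19, 3/19, 1/19, 2/19. They are crude subject percentages, with no exposure beside them.

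**2. Crude incidence under equal rates.** Inputs: the 30-day tail (SAP 13.2), which is 30/30.4375 = 0.986 months; a constant first-event rate λ, the same at both doses (assumed, 0.01 to 0.30 per month); and time on treatment T (assumed, because the documents give none by dose).

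Incidence = 1 − exp(−λ × (T + 0.986)).

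For λ = 0.05: at T = 2, 1 − exp(−0.05 × 2.986) = 13.9%; at T = 6, 1 − exp(−0.05 × 6.986) = 29.5%. The ratio is 2.13 although the rates are equal.

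| λ per month | T = 2 months | T = 6 months | Ratio |
|---|---|---|---|
| 0.01 | 2.9% | 6.7% | 2.29 |
| 0.05 | 13.9% | 29.5% | 2.13 |
| 0.10 | 25.8% | 50.3% | 1.95 |
| 0.20 | 45.0% | 75.3% | 1.67 |
| 0.30 | 59.2% | 87.7% | 1.48 |

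**3. Sensitivity to the assumptions** (ratios from λ = 0.01 to λ = 0.30).
- Smaller differences in treatment time: 2 v 3 months, 1.33 to 1.18; 2 v 4, 1.65 to 1.31; 3 v 6, 1.73 to 1.26.
- Other three-fold differences: 3 v 9 months, 2.43 to 1.36; 4 v 12, 2.50 to 1.26.
- 2 v 6 months as means of exponentially distributed treatment times: 2.25 to 1.37.
- A true three-fold ratio of incidences needs about 3.8 to 4.9 times the treatment time at rates up to 0.05 per month (shorter group 2 or 3 months). At 0.20 per month it is impossible, because the shorter group is already at 45% or more.
- If all events fall in the first weeks, the ratio is near 1.

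**4. What the added summaries show in the same example** (λ = 0.05, 2 v 6 months, 30 subjects per dose).
- Person-time rate: expected first events are 30 × 0.1387 = 4.16 and 30 × 0.2948 = 8.84. Expected person-months to first event or end of window are 4.16/0.05 = 83.2 and 8.84/0.05 = 176.9. Both give 0.05 per month, or 60 per 100 person-years, a ratio of 1.0.
- Onset in Cycles 1-2 (56 days = 1.840 months): 1 − exp(−0.05 × 1.840) = 8.8% at both doses, a ratio of 1.0.

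**5. Chance.** In the protocol's own data, fatigue at 3/18 against 1/19 is a 3.2-fold difference with Fisher p = 0.34. For 0 of 6 subjects the exact 95% CI is 0 to 46%.

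**The case against.** The strongest case against is that the plan delivers what its endpoint asks for. The endpoint is incidence, nature and severity; the study is open-label and descriptive; no test between doses is planned. Most tables also give the number of unique events, and SAP 13.3 gives exposure, so a reader can form a rough rate. Dose-limiting toxicities, which govern escalation and the maximum tolerated dose, already use a common Cycle 1 window (SAP 13.1). In Part A cohorts of 3 to 6, chance swamps any exposure effect.

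Much of this stands, and it limits the point to an improvement. The hand-made rate is a poor substitute, though: unique events include repeats in one subject, and total duration is not time to first event.

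Three stronger readings are tempting, and the documents do not support them.
- A reader might infer that time on treatment does differ by dose. No figures are given, and enrolment order shortens the window only for subjects still on drug at cutoff.
- A reader might infer two- to three-fold distortion. Step 3 shows that doubling treatment time gives at most about 1.7, and that three-fold needs far larger differences.
- A reader might infer that the RP2D choice is undermined. The comparison in Protocol 8.8.4 is within Phase 1b, before any Phase II pooling, and the choice also rests on pharmacokinetics. The SAP 13.2 tables come after it.

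**Conclusion.** The point holds as a low-cost improvement. A primary safety endpoint is tabulated by dose over windows of unequal, open-ended length, and nothing planned separates the event rate from the length of observation.

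The size is conditional. With an assumed three-fold difference in time on treatment (2 against 6 months), the 30-day tail and an equal constant hazard, crude incidences differ about 1.5- to 2.3-fold. The upper end applies to infrequent events. The effect shrinks with smaller differences in exposure and nearly vanishes for early-onset events. In the smallest cohorts sampling error is the larger problem. The direction is firm; the actual amount cannot be known from the documents.

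**What to change.** Keep the crude tables. Add to SAP 13.2, by dose, for any TEAE, Grade 3 or higher, related, serious and AESI:

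- (a) The number and percentage of subjects with an event with onset in Cycles 1-2 (days 1 to 56). Make this the main basis for any statement that compares doses. Report how many subjects were not observed to day 56: those whose last dose came before day 26 (26 + 30 = 56) and those reached by data cutoff.
- (b) The first-event rate per person-time at risk: subjects with a first event, divided by total time to first event, last dose + 30 days or data cutoff, whichever comes first. Give exact Poisson 95% CIs.

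Because dose group is the first dose received, state in (b) that person-time and events are censored at a switch to the RP2D, or show post-switch time and events separately.

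The cost is SAP wording and a few tables from data already collected; study conduct and sample size do not change. The downside of (b) is that it assumes a roughly constant hazard, which is why (a) leads.

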13.3 Extent of Exposure

The analysis will be conducted using SAF set.

Study drug exposure will be summarized using the total number of doses received, total number of cycles, duration of study treatment, relative dose intensity, number of dose interruption, and number of dose reduction. Duration of treatment in weeks is defined as the (last dose date - the first dose date + 1)/7. Relative dose intensity will be calculated as the total amount of dose received divided by (the duration on treatment (in days) × assigned dose). The number of subjects with dose interruption, dose reduction and the reason of dose interruption, dose reduction, the number of dose interruptions and dose reductions will be summarized by frequencies and percentages.

13.4 Clinical Laboratory Evaluation

Local laboratories will be used for laboratory safety evaluations in this study. Laboratory parameters (serum chemistry and hematology) will be summarized using descriptive statistics at baseline and at each post-baseline time point. Changes from baseline will also be summarized.

The following laboratory parameters will be graded according to CTCAE v5.0: hemoglobin, platelets, neutrophils, alkaline phosphatase, AST, ALT, creatinine, glucose, lactate dehydrogenase (LDH), potassium, sodium, and total bilirubin. Shift tables assessing changes from baseline to the maximum post-baseline CTCAE grade will also be presented.

The incidence of CTCAE grade ≥ 3 serum chemistry and hematology results will also be summarized for the parameters listed above.

13.5 Vital Signs

Vital signs (blood pressure, heart rate, respiration, temperature, and weight) will be summarized using descriptive statistics at baseline and at each post-baseline time point. Changes from baseline will also be summarized.

13.6 Electrocardiogram

The Corrected QT interval according to Fridericia's formula (QTcF) and heart rate (HR) from electrocardiogram (ECG) data analysis will be conducted based on methodology recommended in the ICH E14 guideline² (International Council for Harmonisation, 2005).

Descriptive statistics (for the average of the triplicate measurements) at baseline and the maximum of post-baseline as well as changes from baseline will be summarized for QTcF and HR.

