Grade 2 Sinus bradycardia	
 
Hold OP-1250 until resolution to ≤ Grade 1 or baseline and restart 1 dose level lower.
 
If findings recur on 1 dose level lower, hold until resolves to ≤ Grade 1 or baseline and restart at 2 dose levels lower than original dose.
 
If findings recur on 1 dose level lower, hold until resolves to ≤ Grade 1 or baseline and restart at 3 dose levels lower than original dose.
 
If findings recur, discontinue treatment.
 

Grade ≥ 3 Sinus bradycardia	
 
Discontinue treatment.
 

Grade 3 QTc prolongation	
 
Hold OP-1250; address any serum electrolyte abnormalities.
 
Upon resolution of QTcF to ≤ 500 msec, resume OP-1250 at 1 dose level lower.
 
If findings recur, discontinue treatment.
 

Grade 4 QTc prolongation	
 
Discontinue treatment.
 

Worst toxicity NCI-CTCAE, v5.0 a Grade (v5.0)	Recommended dose modifications for OP-1250
Eye Toxicity	
Grade 2 without changes in visual acuity	
 
• Hold OP-1250, contact Medical Monitor, and have ophthalmologist examination. If no concerning findings suggestive of drug effect and resolved to a <math>\leq</math> Grade 1 restart at 1 dose level lower.
 
• If it recurs, hold OP-1250 and contact Medical Monitor. If resolved to a <math>\leq</math> Grade 1, restart at 2 dose levels lower than original dose.
 
• If it recurs again, hold OP-1250 and contact Medical Monitor. If resolved to a <math>\leq</math> Grade 1, restart at 3 dose levels lower than original dose.
 

Grade 2 with changes in visual acuity Grade 3 or 4	
 
• Discontinue treatment.
 

Neurologic Toxicity	
Grade 2 Headache	
 
• If AE occurs that is not relieved with supportive care for 7 days the investigator or designee can reduce 1 dose level.
 
• If AE occurs that is not relieved with supportive care for 7 days the investigator or designee can reduce 1 additional dose level.
 
• If AE occurs that is not relieved with supportive care for 7 days the investigator or designee can reduce 1 additional dose level.
 

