#### 11.2.1 Electrocardiogram Analyses

The analysis of ECG results will be based on subjects in the SAF with baseline and on treatment ECG data.

ECG measurements (an average of the triplicate measurements) will be used for the statistical analysis and all data presentations. Any data obtained from ECGs repeated for safety reasons after the nominal time-points will not be averaged along with the preceding triplicates. Interval measurements from repeated ECGs will be included in the outlier analysis (categorical analysis) as individual values obtained at unscheduled time points.

QT intervals will be corrected for heart rate, QTc, using standard correction factors (ie, Fridericia's [default correction], Bazett's, and possibly a study specific factor, as appropriate). QTcF will be calculated using the Fridericia formula, as follows:

$$QT_{cF} = \frac{QT}{\sqrt[3]{RR}}$$

Data will be summarized and listed for QT, heart rate, RR interval (RR), PR, QRS, QTc and by study arm and dose. Individual QT (all evaluated corrections) intervals will be listed by study arm time and dose. The most appropriate correction factor will be selected and used for the following analyses of central tendency and outliers and used for the study conclusions. Descriptive statistics (n, mean, median, standard deviation, minimum, and maximum) will be used to summarize the absolute corrected QT interval, and changes from baseline in corrected QT after treatment by study arm dose and time point. For each subject and by treatment, the maximum change from baseline will be calculated as well as the maximum post-baseline interval across time points. Categorical analysis will be conducted for the maximum change from baseline in corrected QT and the maximum post-baseline QT interval.

Changes from baseline for the ECG parameters QT interval, heart rate, RR, QTc, PR interval, and QRS interval will be summarized by treatment and visit (time).

The number (percent of subjects with maximum post-dose QTc values and maximum increases from baseline in the following categories will be tabulated by treatment:

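### SAP 13.6 summarises ECG heart rate by each subject's post-baseline maximum, the wrong extreme for bradycardia, and drops the by-visit ECG heart-rate summary planned in protocol 11.2.1 (minor)

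*SAP*

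**What the plan says.** SAP 13.6 (Electrocardiogram) covers two parameters in one sentence. Descriptive statistics of the triplicate average "at baseline and the maximum of post-baseline as well as changes from baseline will be summarized for QTcF and HR". It mentions no minimum, no low-rate category and no summary by time point.

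The Cardiac block of protocol Table 8 contains "Grade 2 Sinus bradycardia" (hold and reduce), sinus bradycardia of Grade 3 or higher (discontinue) and QTc prolongation, beginning with "Grade 3 QTc prolongation". It has no row for a fast heart rate.

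Protocol 11.2.1 treats the two parameters differently. For the QT interval: "Categorical analysis will be conducted for the maximum change from baseline in corrected QT and the maximum post-baseline QT interval". For the wider set of ECG parameters, changes from baseline in "heart rate, RR, QTc, PR interval, and QRS interval will be summarized by treatment and visit (time".

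SAP 13.5 covers heart rate as a vital sign: "Vital signs (blood pressure, heart rate, respiration, temperature, and weight) will be summarized using descriptive statistics at baseline and at each post-baseline time point", with changes from baseline. SAP 6.2 defines descriptive statistics to include the mean, the minimum and the maximum. SAP 13.2 tabulates adverse events by preferred term and maximum grade, and those leading to discontinuation, dose reduction or withheld drug.

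**The concern.** A per-subject maximum picks each subject's fastest reading. Even with no drug effect it lies above the subject's usual rate, and it rises with the number of ECGs taken. If the drug slows the heart, this upward bias offsets part or all of the fall in the table. The trial has no comparator from which the bias could be subtracted. It also differs between subjects with different time on treatment, because they contribute different numbers of ECGs.

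Safety and tolerability are a primary objective in both phases, and sinus bradycardia is one of the events for which the protocol holds or stops treatment. At stake is whether the triplicate ECG data, already collected at fixed times that include 4 hours post-dose, will be tabulated in a way that can show slowing.

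**Working it through.** The documents give no figure for this point, so there is none to reproduce. The check has four steps.

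**1. Number of readings.** Protocol Table 2 gives these scheduled post-baseline ECGs: C1D1 at 4 h, C1D2, C1D8, C1D15, C2D1 pre-dose, C2D1 at 4 h, then C3, C5, C7 and C9. That is k = 10 through C9, and k = 6 for a subject who stops after Cycle 2.

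**2. Size of the bias.** For k independent normal readings with within-subject SD s, the expected maximum exceeds the subject's own mean by c × s, where c = 1.267 for k = 6 and c = 1.540 for k = 10. Baseline is not selected as an extreme, so it adds no bias on average. With a true sustained change d:

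mean change at the maximum = d + c × s

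mean change at the minimum = d - c × s

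mean change at any one visit = d

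The documents give no value for s. The values 4, 6 and 8 bpm are assumptions.

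**3. A sustained fall of 10 bpm (d = -10).**

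| Assumed s (bpm) | At maximum, k = 10 | At maximum, k = 6 | Any single visit |
|---|---|---|---|
| 4 | -10 + 6.2 = -3.8 | -10 + 5.1 = -4.9 | -10 |
| 6 | -10 + 9.2 = -0.8 | -10 + 7.6 = -2.4 | -10 |
| 8 | -10 + 12.3 = +2.3 | -10 + 10.1 = +0.1 | -10 |

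With no drug effect and k = 10, the maximum shows +6.2, +9.2 and +12.3 bpm, and the minimum shows the same values with a negative sign. By-visit means carry no such bias.

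**4. A fall of 15 bpm at the two 4-hour ECGs only (k = 10).** By simulation of 200,000 subjects, the mean change at the maximum is +5.7, +8.6 and +11.4 bpm for s = 4, 6 and 8. With no effect it is +6.2, +9.3 and +12.3. The two sets differ by 0.5, 0.7 and 0.9 bpm, so the maximum hardly distinguishes them. The mean at the 4-hour time point shows -15.

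**Could vital-sign heart rate stand in for the 4-hour ECG?** Protocol Table 1 lists vital signs by visit day without post-dose times and, as far as the extracted table can be read, has none on C1D2. Protocol 10.2.5 places ECGs before vital signs. That fixes the order when both are taken, but it does not require vital signs at 4 hours.

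**The case against.** The strongest reply is that slowing would be seen elsewhere, and for most forms of slowing this is right. SAP 13.5, read with SAP 6.2, gives vital-sign heart rate at each visit with its mean, its lowest value and its change from baseline. Bradycardia reported as an adverse event is tabulated by grade, and so are the resulting holds, reductions and discontinuations. A reader might infer from SAP 13.6 that the safety analysis as a whole conceals bradycardia; the documents do not support that. What these tables leave open is slowing limited to the 4-hour post-dose ECGs and not reported as an adverse event. The visit-level minimum in SAP 13.5 is the lowest value in the dose group at that visit. It is neither each subject's own lowest value nor a count of subjects with low rates.

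Second, the reference in SAP 13.6 to changes from baseline is ambiguous. If it means change at each time point, the table would show slowing. SAP 13.4 and 13.5 both specify each post-baseline time point and 13.6 does not, which favours reading it as change at the maximum but does not settle it. SAP 13.6 also cites an external guideline, which is not available here and was not relied on.

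Third, the bpm figures rest on assumed SDs and independent readings. Positive correlation between readings, beyond the subject's own level, would shrink the bias without changing its direction. A reader might infer that real slowing would always appear as no change or a rise. For a 10 bpm fall, the sign reverses only at the largest SD considered; at 4 bpm the fall is reduced to about 4 or 5 bpm.

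Fourth, bradycardia is not singled out elsewhere as a leading risk. The protocol's risk summary does not mention it, and the events of special interest are Grade 4 neutropenia terms. A fast heart rate would fall under the general non-hematologic rows of Table 8. This tempers the importance of the point, but sinus bradycardia remains the only heart-rate event with its own rows.

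**Conclusion.** The point holds as a minor one. SAP 13.6 applies a QTcF statistic to heart rate, where it selects the wrong extreme for the only named heart-rate toxicity, and it does not carry over the by-treatment, by-visit ECG heart-rate summary of protocol 11.2.1. Reading its changes as taken at the maximum, and assuming independent readings with SDs of 4 to 8 bpm, a sustained 10 bpm fall would appear as about -4 to +2 bpm with 10 time points, and about -5 to 0 with 6.

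The defect is limited to the ECG heart-rate table. Two gaps remain after the other tables are counted: slowing at the 4-hour post-dose ECGs has no assured counterpart, and neither document plans a per-subject minimum or a low-rate count. Efficacy, dose decisions and dose-limiting toxicity rules are not affected.

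**What to change.** In SAP 13.6, separate heart rate from QTcF.

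- Keep the post-baseline maximum for QTcF.
- For ECG heart rate, summarise values and changes from baseline by dose and time point, as protocol 11.2.1 plans, with the 4-hour post-dose time points shown separately.
- Report each subject's minimum post-baseline heart rate and largest decrease from baseline, in place of the maximum or beside it.
- Count subjects whose minimum falls below cut-offs fixed before database lock. These serve reporting only and change no treatment rule.

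The cost is a few lines of SAP text and one revised table shell, using ECG data already collected. There is a small downside. In a single-arm study the minimum is biased downward by chance, by about 6 to 12 bpm with no drug effect under the same assumptions (k = 10), so it must be read beside the by-time-point means. If the maximum is dropped altogether, the per-subject upward extreme is no longer shown; keeping it beside the minimum avoids that.
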